13.10 Occupational Exposure

Occupational exposure refers to the exposure to a medicinal product as a result of one's professional or non-professional occupation and will be reported in a manner identical to the reporting of SAEs, however via the use of an occupational exposure form instead of a SAE form.

Occupational exposure with or without an AE, should be reported within 24 hours of becoming aware of the exposure.

14. Statistical Methods

A Statistical Analysis Plan will be prepared prior to the first interim analysis. Overall principles are described below.

14.1 Sample Size Calculation

No formal sample size calculation was made. The choice of 5 to 7 subjects in each cohort is considered sufficient to capture commonly occurring AEs ([Percy et al., 2010](#)).

14.2 Statistical Methods

All reporting will be made for the Full Analysis Set. Reporting may be made for other analysis populations, or subgroups of subjects based on for example genotype.

Data will be presented in tables and listings following the principles in [ICH E3 guideline](#) regarding structure and content of clinical reports. Data will also be presented graphically by subject and for selected endpoints all data will be presented.

Summary tables will show number of values and when applicable number of missing values.

Categorical data will be presented with number of cases and percentage of total number of cases. Continuous data will be presented with mean and SD, median, minimum and maximum as appropriate.

Continuous data will be shown in listings with the same precision as captured.

Subject level summaries will be presented adjusted for observation time. This includes but is not limited to annualized rate of selected signs and symptoms, annualized bleeding rate, average value for laboratory parameter or area under the time-profile curve normalized with time.

Laboratory parameters will be presented by visit and include categorization of parameters into low/normal/high where applicable.

Prophylactic and on-demand FIX replacement therapy will be summarized according to type of medication. Other concomitant treatment will be presented by therapeutic grouping presenting number of subjects and number of treatments.

No formal statistical hypothesis will be tested. All confidence intervals represent exploratory analyses and will not be related to formal statistical hypothesis tests. No correction for multiplicity will be applied.

14.2.1 Primary Efficacy Endpoint Analysis

AEs will be coded using Medical Dictionary for Regulatory Activities (MedDRA) and summarized by system organ class and preferred term presenting the number of subjects and number of events. Furthermore, summary tables will be made presenting severity for each event, and using the maximal severity for event. Separate summaries will be made for selected AEs.

Clinical Trial Protocol

Trial ID: CT-AMT-060-01

uniQure

14.2.2 Secondary Efficacy Endpoint Analysis

FIX Levels in Plasma

Data will be presented by subject, time point and dose level as summary tables and graphically.

Adjustment for time since most recent administration of FIX replacement therapy may be made, for example reporting by time less than 72 hours versus more than 72 hours after (reflecting prophylaxis free assessment). If applicable, the presentation will include summary statistics and confidence intervals for difference in FIX concentration between time-periods.

If applicable, the FIX level will be analysed using Non-Linear Mixed Models, possibly after transforming the data, and may include subject level random effect or subject level covariate to describe dependency between measurements. The analysis may include information on dose and timing of FIX replacement therapy. If relevant, the analysis may be extended to include modelling of values below lower level of quantification. The modelling may include subject level information on type of FIX replacement therapy, half-life, and if available previous knowledge of subject specific half-life for the FIX replacement therapy.

Number, Severity and Type of Bleeding Episodes

Bleeding episodes will be summarized by subject and overall, and will include number, duration and severity. Separate summaries may be made for bleeds depending on type and location, including target joints, and also summaries excluding recurrent bleeds.

Annualized bleeding rates overall and by severity will be presented. If relevant, summaries will be made using timing representing subject specific periods for pre-tapering, tapering period, and post tapering period until 26 weeks, and post 26 weeks.

Furthermore, the number of bleedings may be analysed using models for count data adjusting for time at risk using generalized linear model with Poisson or Negative Binomial distribution. Where description of timing and inter-event duration is of interest, models for time-to-event analysis may be used, such as Cox Proportional models or other parametric model, possibly including subject level frailty parameter. The analysis may include information on dose and timing of FIX replacement treatment, and measured FIX concentration.

Prophylactic and On-demand FIX Replacement Therapy

The use of prophylactic and on-demand FIX replacement therapy in general will be summarized by subject and overall. If relevant, summaries will be made using timing representing subject specific periods for pre-tapering, tapering period, and post tapering period until 26 weeks, and post 26 weeks.

14.2.3 Patient Reported Outcome Data

For **CCI**, the scale scores will be listed by subject and visit and summarized as appropriate.

Clinical Trial Protocol

Trial ID: CT-AMT-060-01

uniQure

14.3 Subject Population(s) for Analysis

The Full Analysis Set will consist of all dosed subjects and will be used for reporting. If applicable, further analysis sets will be defined, such as a Per Protocol Analysis set.

14.4 Significance Level

No formal statistical testing will be performed. Unless otherwise noted statistical tests will be reported using a significance level of 0.05. Confidence intervals will be presented as 95% 2-sided confidence intervals.

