8.2.2 Secondary Endpoints

Secondary endpoints will be addressing efficacy and safety:

Confirmatory Secondary Efficacy Endpoint

- FIX-replacement-therapy-free FIX activity^{1, 2}

Supportive Efficacy Endpoints

- Bleeding rate
- Total consumption of FIX replacement therapy
- CCI scores

¹ Definition of FIX-replacement-therapy-free FIX activity: FIX activity measured any time from 72 hours after latest FIX replacement therapy administration and until next administration of FIX replacement therapy, if any

² FIX activity will be measured with both the one-stage aPTT assay and the amidolytic/chromogenic assay.

Clinical Trial Protocol

Trial ID: CT-AMT-060-01

uniQure

Safety Endpoints

- Vector DNA in semen, blood, saliva, nasal secretions, urine and faeces
- Neutralizing antibodies to AAV5
- Total (IgM and IgG) antibodies to AAV5
- AAV5 capsid-specific T cells
- Antibodies to FIX
- FIX inhibitors
- Inflammatory markers: IL-1 β , IL-2, IL-6, INF γ , MCP-1

Clinical Trial Protocol

Trial ID: CT-AMT-060-01

uniQure

9. Trial Population

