10.4 Rationale for Trial Design

A dose ascending design is chosen to determine the safety and tolerability of 2 dose levels.

As a secondary objective, the trial design supports the scope to explore the maximum achievable bioactivity of AAV5-hFIX as assessed by FIX-replacement-therapy-free FIX activity levels at the 2 dose levels.

The objective for the first cohort is to explore whether 5×10^{12} gc/kg can achieve therapeutically relevant bioactivity levels of >2% of FIX-replacement-therapy-free FIX activity without safety concerns.

The objective for the second cohort is to explore whether 2×10^{13} gc/kg can achieve an expression level of FIX in the range of 5-10% of FIX-replacement-therapy-free FIX activity without safety concerns.

The design is based upon the non-clinical data (see [Section 6.6.2](#)) and the available data from prior clinical experience with similar AAV-vector based gene therapy products (see [Section 6.6.3](#)) that supports that safe and therapeutically relevant expression levels of FIX may be anticipated with AAV5-hFIX at one or both of the 2 dose levels (see also the dose rationale in [Section 10.5](#)).

To support subject safety, the trial is designed with 2 consecutive dose arms with ascending doses and data monitoring committee review before start of dosing in the next cohort. Subjects are therefore not randomly assigned to the 2 arms, which introduces a risk of selection bias. Part of this risk will be mitigated by strict adherence to inclusion and exclusion criteria and in addition only 2 subjects with moderately severe haemophilia will be allowed in each cohort thereby preventing that the moderately severe subjects are allocated to the lowest dose level only.

Clinical Trial Protocol

Trial ID: CT-AMT-060-01

uniQure

Due to the nature of the disease in question it is not ethical to perform a placebo-controlled trial and no relevant active comparators exist. Based on this the trial is designed as an open-label and uncontrolled trial.

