Confirmatory Secondary Efficacy Endpoint: FIX-replacement-therapy-free FIX activity.

Supportive Efficacy Endpoints:

- Bleeding rate
- Total consumption of FIX replacement therapy

The secondary objectives in relation to safety are stated as:

- To monitor shedding of the AAV5 vector in various body matrices
- To monitor the immune responses against AAV5 capsid proteins in response to AAV5-hFIX
- To monitor for immune responses against FIX protein after administration of AAV5-hFIX
- To investigate the effect of AAV5-hFIX on inflammatory markers

Consequently, the secondary safety end points are the following:

- Vector DNA in semen, blood, saliva, nasal secretions, urine and faeces
- Neutralizing antibodies to AAV5
- Total (IgM and IgG) antibodies to AAV5
- AAV5 capsid-specific T cells
- Antibodies to FIX
- **FIX** inhibitors

Larix A/S - Strictly Confidential F501-0-1-5 SAP Template Page 7 of 34

Date: 27MAY2021

Final no. 05

Page 8 of 34

CT-AMT-060-01 EudraCT No.: 2013-005579-42 Statistical Analysis Plan

- Inflammatory markers IL-1β, IL-2, IL-6, INFγ, MCP-1

Larix A/S - Strictly Confidential F501-0-1–5 SAP Template Page 8 of 34

Date: 27MAY2021

CT-AMT-060-01 EudraCT No.: 2013-005579-42

Statistical Analysis Plan

Final no. 05 Page 9 of 34

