The distance between a FIX activity measurement and the latest FIX replacement therapy administration preceding the FIX activity measurement in question (c.f. section 4.4.2.1) is calculated as follows:

- date(FIX activity measurement) - date(preceding FIX replacement therapy administration) + 1

The date and time of the FIX activity measurement in question and the FIX replacement therapy administrations respectively are used to find the latest FIX replacement therapy administration preceding

Larix A/S - Strictly Confidential F501-0-1–5 SAP Template Page 13 of 34

•
ariv

CT-AMT-060-01 EudraCT No.: 2013-005579-42 Statistical Analysis Plan

Final no. 05 Page 14 of 34

the FIX activity measurement in question. In case the dates of the FIX activity measurement in question and a FIX replacement therapy administration are the same and no time is indicated, it is assumed that the FIX replacement therapy administration precedes the FIX activity measurement in question, and the above defined distance therefore becomes equal to 1 (see also section 4.4.2.1).

Duration of an AE in days is calculated (when possible) as date(Resolution) - date(Onset) + 1.

Date: 27MAY2021

No formal statistical hypothesis will be tested. Two-sided 95% confidence intervals may be calculated but these intervals represent exploratory analyses and will not be related to formal statistical hypothesis tests. No correction for multiplicity will be applied.

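### FIX-free activity is labelled confirmatory in a purely descriptive plan; the levels each cohort is meant to explore (>2%, 5-10%) are never counted, and the by-visit FIX-free summaries lean towards subjects with adequate expression

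*Protocol*

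**What the plan says.** **Label.** Protocol 8.2.2 places the endpoint alone under "Confirmatory Secondary Efficacy Endpoint", apart from the supportive endpoints. SAP section 1 repeats it: "Confirmatory Secondary Efficacy Endpoint: FIX-replacement-therapy-free FIX activity".

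**Inference.** Protocol 14.2 states: "No formal statistical hypothesis will be tested. All confidence intervals represent exploratory analyses and will not be related to formal statistical hypothesis tests". SAP 4.1 agrees: "No formal statistical hypothesis will be tested. Two-sided 95% confidence intervals may be calculated", again as exploratory. Both rule out a multiplicity correction. Protocol 14.4 reads: "No formal statistical testing will be performed. Unless otherwise noted statistical tests will be reported using a significance level of 0.05", and then "Confidence intervals will be presented as 95% 2-sided confidence intervals".

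**Levels.** Protocol 10.4 has Cohort 1 explore whether its dose "can achieve therapeutically relevant bioactivity levels of >2% of FIX-replacement-therapy-free FIX activity", and Cohort 2 whether its dose reaches 5-10%.

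**Planned displays.** For each central-laboratory assay, SAP 4.4.2.1 lists every value with the days since last FIX. It also summarises values by visit and cohort, once for all values and once for FIX-free values only. Table shells 14.2.1 to 14.2.4 show n, mean (SD), median, minimum, maximum and CV. For the one-stage aPTT assay only, there are individual FIX-free profiles after tapering, with regression lines and 95% intervals per patient.

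**What counts as FIX-free.** Protocol 8.2.2 uses 72 hours since last FIX. SAP 4.4.2.1 uses more than 10 days, and SAP section 6 declares the change.

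**The concern.** A confirmatory label tells the reader that a prespecified claim will be accepted or rejected. Nothing in this plan can do that, and the 0.05 sentence in 14.4 would give cover to any nominal p-value produced later.

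The second problem matters more for the results. The protocol says which activity level each dose is meant to explore, but the reader of the report will get no statement of how many dosed subjects reached it. The by-visit FIX-free mean is the nearest substitute. It is computed over whoever is off FIX at that visit, and for prophylaxis subjects being off FIX is itself governed by a 2.0% activity rule. A favourable mean could then partly reflect who remained in the table.

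**Working it through.** **1. Label against design.** The documents give no power, effect size or decision rule for this endpoint, so there is no design figure to reproduce. A confirmatory analysis needs at least a null value, a test or decision rule, a time point and a deciding assay. Protocol 8.2.2, 10.4, 14.1, 14.2, 14.2.2 and 14.4, and SAP 1, 2.2, 4.1 and 4.4.2.1, name none of these. Protocol 14.1 bases 5 to 7 subjects per cohort on capturing common adverse events.

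**2. Section 14.4 against itself and the SAP.** The first sentence excludes formal testing; the second sets a level for tests. SAP 4.1 keeps the first statement ("No formal statistical hypothesis will be tested") and does not carry the 0.05 level. SAP section 6 lists only the move from 72 hours to 10 days as a deviation, so the 0.05 sentence is not expressly withdrawn.

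**3. Levels against displays.** No text in SAP 4.4.2.1 and no row in shells 14.2.1 to 14.2.4 refers to 2% or 5-10%. A mean does not stand in for a count. The six high-dose subjects of the earlier AAV8 trial (Protocol Table 6-3) had 3.56, 7.21, 5.00, 6.67, 5.23 and 2.89%:

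- Sum 30.56; mean 30.56/6 = 5.09%, SD 1.69. This matches the 5.1 and 1.7 that Protocol 6.6.3 quotes.
- The mean lies inside 5-10%, but only 4 of 6 subjects do. All 6 exceed 2%.

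**4. How subjects enter and leave the FIX-free summary.**

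- Protocol 11.4: tapering starts only after activity of at least 2.0% at the two previous visits, and each step and continued withholding require the same.
- Protocol 11.4: prophylaxis restarts if activity is below 2.0%. The investigator may also restart it at any time for medical reasons.
- Protocol 6.2 describes prophylaxis as infusions 2-3 times a week. On such a regimen the gap between doses never exceeds 10 days.
- SAP 4.4.2.1 counts a value as FIX-free only more than 10 days after the last dose.

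A prophylaxis subject who never qualifies to taper, or who falls below 2.0% and restarts at that frequency, contributes no FIX-free value while on it. The 2.0% rule uses the local laboratory and the tables use the central one, so the selection acts through a related measurement, not the identical one.

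**5. Direction, by illustration only.** Assume four prophylaxis subjects with the values of the four subjects below the high dose in Table 6-3: 2.17, 1.4, 2.86 and 2.17%.

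| | n | Mean | Minimum | Above 2% |
|---|---|---|---|---|
| All four | 4 | 8.60/4 = 2.15% | 1.4% | 3 of 4 |
| After the 1.4% subject restarts FIX | 3 | 7.20/3 = 2.40% | 2.17% | 3 of 3 |

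Mean and minimum both rise and the shortfall disappears from view. These are another trial's values, so they show direction, not size.

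**6. Precision of a count.** Exact (Clopper-Pearson) 95% limits for x of n are the 0.025 quantile of Beta(x, n-x+1) and the 0.975 quantile of Beta(x+1, n-x). When x = n the lower limit is 0.025^(1/n).

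| Result | Exact 95% CI |
|---|---|
| 5/5 | 0.025^(1/5) = 47.8% to 100% |
| 4/5 | 28.4% to 99.5% |
| 3/5 | 14.7% to 94.7% |
| 7/7 | 0.025^(1/7) = 59.0% to 100% |

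**The case against.** **No test is coming.** A reader might infer that 14.4 commits the trial to a series of tests at 0.05 over many visits and two assays, with inflated false positives. The documents do not support that. The sentence is default wording that names no test, null value or endpoint. The optional models in Protocol 14.2.2 could yield p-values, but the SAP schedules none of them, and the FIX shells hold no p-value. An error rate for independent tests would not fit anyway, since the values are repeated measurements on about five subjects per cohort. This stands: the fault in 14.4 is one of wording.

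**The endpoint is analysed.** A reader might also infer that FIX-free activity is reported only as means. It is not: every value is listed, and minimum, maximum and individual aPTT profiles are planned. With five subjects a reader can work out much by hand. This stands in part. The minimum covers only subjects with a FIX-free value at that visit, and the profiles plot FIX-free values only, so neither shows who is absent or why.

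**A responder count is not the stated estimand.** Protocol 10.4 is rationale text about what a dose can achieve, and the formal objective in 8.1.2 is the effect on activity level. Fair; the count is therefore proposed as an added description, not as a replacement endpoint.

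**Counting subjects on FIX as not reaching the level can misclassify.** Someone kept on FIX for other medical reasons may express well. This stands, and is why those subjects need their own row.

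**It would be post hoc.** The trial is open-label, with interim cut-offs of 5 August 2016 and 12 May 2017 (SAP Appendix 1), and the current SAP is dated 27 May 2021. This stands and must be disclosed.

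**Conclusion.** The concern holds as a labelling fault plus a gap in the descriptive analysis. The endpoint is not confirmatory under either document, and 14.4 contradicts itself. The levels in 10.4 are compared with nothing, and the FIX-free by-visit summaries are selected towards adequate expression among prophylaxis subjects.

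The size of the selection cannot be derived. It depends on how many subjects stay on or return to FIX, which the documents do not give. The direction rests on two assumptions: that the 2.0% rule in 11.4 is followed, and that prophylaxis runs at about the frequency in Protocol 6.2.

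It would be wrong to conclude that the trial needed a hypothesis test. This is a first-in-human trial with adverse events as the primary endpoint, and descriptive efficacy is appropriate. With five subjects even a perfect result leaves a lower limit of 48%, which is a further reason not to call the endpoint confirmatory. The tapering and restart rules matter here only because they decide who has evaluable data; they are not judged.

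**What to change.** 1. Protocol 14.4: delete the sentence setting a 0.05 level for tests.
2. Protocol 8.2.2 and SAP section 1: relabel the endpoint *key secondary (descriptive)*.
3. SAP 4.4.2.1: add one descriptive table per cohort and assay, with all dosed subjects as denominator. Give the number whose mean FIX-free activity in each trial year is >2% (Cohort 1), or is >=5% and, separately, within 5-10% (Cohort 2), with exact 95% intervals. Draw values through Visit 35; FIX-free shells 14.2.2 and 14.2.4 now run to Visit 26.
4. Use the SAP window of more than 10 days, with the protocol's 72 hours as a sensitivity analysis.
5. Show subjects with no FIX-free value because they remained on or returned to FIX in a separate row, counted as not shown to reach the level.
6. State that the table was added after the 2016 and 2017 interim cut-offs.

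The cost is two wording changes and one small table from data already collected. The confirmatory label is given up, and a subject kept on FIX for other medical reasons may be counted as not reaching the level. The separate row lets the reader see how many that could be.

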14.5 Termination Criteria

Not applicable, as no formal procedure based on statistical decision rules is defined.

14.6 Handling of Missing Data

All data will be listed, including unused and spurious data. Imputation of missing or partial data will not be done unless explicitly described. In case of imputation of missing data, both the original missing or partial data and the imputed values will be listed.

14.6.1 Handling of Missing Data for Bleeding Episodes

Bleeding episodes will be recorded with start and end date and time. A bleeding episode is classified as a re-bleed, if there is less than 72 hours between start and stop of previous episode (definition of re-bleed in [Section 12.1.2](#)). In case of partial start and stop date, the classification will be made using a conservative approach.

14.7 Deviation Reporting

Deviation(s) from the planned statistical analysis plan will be described and justified in the protocol and/or in the final CSR.

14.8 Interim Analysis

Interim analyses will be performed at the request of the data monitoring committee and at the request of the sponsor to enable reporting of adequate data at selected time points during the course of the trial. Descriptive statistics alone will be used for the interim analyses.

Formal interim analyses will occur after all subjects have been followed for at least 12 weeks (i.e. completed Visit 14) and at least 52 weeks (i.e. completed Visit 23). The data from the 52-week analyses will be reported in an interim CSR.

Clinical Trial Protocol

Trial ID: CT-AMT-060-01

uniQure

15. Data Monitoring Committee

A data monitoring committee will be established to:

- perform on-going safety surveillance throughout the entire trial period
- evaluate available safety data from the first subject in each cohort and provide a recommendation to the sponsor regarding dosing of the second subject
- evaluate available safety data from the second subject in each cohort and provide a recommendation to the sponsor regarding dosing of the subsequent subjects in a cohort
- evaluate available safety data from subjects in Cohort 1 and provide a recommendation to the sponsor regarding dosing of subjects in Cohort 2

The data monitoring committee's review of available data prior to dosing of subjects within each cohort as well as between cohorts may reveal safety issues requiring further investigation prior to dosing of the next subject(s). The data monitoring committee will align their recommendation(s) with the Trial Stopping Rules as given in [Section 19.2](#).

The data monitoring committee will consist of at least 2 external and independent experts, of which one will be the chairman. In addition, at least one of the external independent experts should be medically qualified.

Details on the composition, tasks and responsibilities of the data monitoring committee will be described in the [data monitoring committee charter](#).

Clinical Trial Protocol

Trial ID: CT-AMT-060-01

uniQure

16. Ethics

